10.3.3. Additional Analysis of IARs

10.3.3.1. Analysis by Onset Intervals

The onset intervals (in months), defined relative to the first dose of the 20 mg/kg ATB200 + 260 mg AT2221 study drug, will be: ≤ 6 , > 6 to ≤ 12 , > 12 to ≤ 18 , > 18 to ≤ 24 , and > 24 . For Cohort 1 subjects, the first dose of the 20 mg/kg ATB200 + 260 mg AT2221 study drug happened in Stage 2 Period 5.

The event rates and changes in intensity over time (over these intervals) will be summarized. This analysis will further describe the clinical characteristics of IARs, and it can help determine whether the IARs disappear over time or appear late.

10.3.3.2. Analysis of Time to First IAR-TEAE

The number of subjects with IARs and the onset dates of the IARs are already available in the database. For each of these subjects, the time (in weeks) starting from the first dose of the 20 mg/kg ATB200 + 260 mg AT2221 study drug to the onset of the first TEAE that is an IAR (ie, IAR-TEAE) will be calculated as: Time to first IAR-TEAE (weeks) = (date of the first IAR-TEAE while using the 20 mg/kg ATB200 + 260 mg AT2221 dose – date of first dose of the 20 mg/kg ATB200 + 260 mg AT2221 study drug + 1) / 7.

This analysis does not include subjects who have no IARs. The calculated times will be summarized as described in Section [6.2.1](#) to obtain the mean time to the first IAR-TEAE.

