6.4.2.6. ATB200 Preliminary Efficacy Data

The fourth interim analysis was conducted in September 2017 with data cut-off point in August 2017.

Adverse events (AEs) were generally mild and transient. Most common AEs reported as treatment related were nausea (3/20), tremor (3/20), headache (3/20), fatigue (3/20), diarrhea (2/20), muscle spasm (2/20), and joint swelling (2/20). Three incidents of infusion-associated reactions (IARs) in 400⁺ infusions which were controlled by standard premedication. One IAR event occurred in one nonambulatory ERT-switch patient (skin discoloration). Two IAR events in an ERT-naïve patient (localized pruritus, erythema and burning sensation). Longest duration of treatment was 72 weeks.

Improvement in biomarkers of muscle damage (creatine phosphokinase [CK], alanine aminotransferase [ALT], and aspartate aminotransferase [AST]) and disease substrate (hexose tetrasaccharide [Hex4]) was observed for up to 58 Weeks on ATB200/AT2221 in all three cohorts.

Six-minute walk distance improved in Cohorts 1 and 3 as shown in [Table 6](#). Qualitative and quantitative upper extremity muscle strength improved in Cohort 2 subjects. Forced vital capacity was stable in Cohort 1 and improved in Cohort 3 as shown in [Table 7](#).

Table 6: Change in 6MWT Distance in Meters in Cohorts 1 and 3 Subjects Through Month 18

Cohort	Mean (SD)	Mean (SD) Change from Baseline			
	Baseline	Month 6	Month 9	Month 12	Month 18
1^a ERT-experienced (2 to 6 years)	(n = 10) 397.2 (96.8)	(n = 10) +23.9 (52.2)	(n = 10) +24.5 (40.8)	(n = 10) +42.2 (46.5)	(n = 9) +51.7 (45.9)
3 ERT-naïve	(n = 5) 399.5 (83.5)	(n = 5) +41.8 (29.4)	(n = 5) +63.5 (23.1)	(n = 5) +63.1 (29.1)	(n = 5) +49.0 (28.3)

Abbreviations: 6MWT = 6-minute walk test; ERT = enzyme replacement therapy; n = number of patients; SD = standard deviation

^a For the purposes of assigning nominal time points to data from Cohort 1, the 6-week duration of Stage 1 (single ascending doses of miglustat) and the 12-week duration of Stage 2 (multiple ascending doses of miglustat [130 mg for 6 weeks, followed by 260 mg for 6 weeks]) were included. Therefore, the Month 6, 9, 12, and 18 time points reflect cumulative data to Stage 3 Month 3, Stage 3 Month 6, Stage 3 Month 9, and Stage 3 Month 15, respectively.

Source: Interim Analysis 6 (data cut-off date of August 2018), Table 14.2.1.3

Table 7: Change in Percentage Predicted Sitting FVC (%) in Cohorts 1 and 3 Subjects Through Month 18

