2. INTRODUCTION

This statistical analysis plan (SAP) is based on Amendment 8 to Protocol ATB200-02 dated 10 January 2019. The purpose of this SAP is to describe the planned data analyses and outputs to be included in the final clinical study report (CSR) to close out the study. Most of the subjects in Study ATB200-02 are expected to transition to commercial products while a few will transition to the sponsor's expanded access program (EAP) Study ATB200-11. The expected database lock (DBL) date for the final CSR is 24 July 2024.

The study design consists of 4 stages as described in Section 5 (and represented in Table 2), and the stages are as follows:

- Stage 1 involves the administration of a single-ascending dose (SAD) of ATB200 (also referred to as cipaglucosidase alfa) alone, with focus on safety, tolerability, and pharmacokinetic (PK) assessments.
- Stage 2 involves the co-administration of multiple-ascending doses (MAD) of ATB200/AT2221 (also referred to as cipaglucosidase alfa/miglustat), with a focus on safety (including pharmacodynamics [PD]) and PK assessments.
- Stages 3 and 4 involve a fixed dosing regimen of ATB200/AT2221 co-administration to support the proof of concept and the long-term extension phase of the study (with long-term efficacy and safety assessments).

The ATB200-02 study data have been reported previously in 2 interim clinical study reports and 1 addendum. The first interim clinical study report (iCSR-1), dated 15 December 2020, was based on the data cutoff date of 19 June 2020 and focused mainly on the analyses of the study data during Stages 1 and 2, including the complete analysis of the PK data, as well as the safety and PD data collected prior to the co-administration of the fixed dosing regimen of 20 mg/kg cipaglucosidase alfa + 260 mg miglustat. An addendum to iCSR-1, dated 11 May 2021, was based on the data cutoff date of 13 November 2020. The second interim clinical study report (iCSR-2), dated 31 August 2022, focused on the analysis of long-term efficacy, PD, immunogenicity (IMG), and safety data collected during Stage 2 Period 5 through Stages 3 and 4 that were available at the time of the data cutoff date of 13 December 2021.

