5. STUDY DESIGN

5.1. Summary of Study Design

This is an open-label, fixed-sequence, single- and multiple-ascending dose, first-in-human (FIH) study to evaluate the safety, tolerability, PK, PD, and efficacy of intravenous ATB200 alone and when co-administered with oral AT2221. The study was conducted in 4 stages and enrolled 4 cohorts as shown in [Table 2](#).

The 4 cohorts in the study are as follows:

- Cohort 1: this cohort was planned to enroll 11 ERT-experienced ambulatory subjects defined as adults with Pompe disease who have been on ERT for 2 to 6 years prior to enrollment and are able to walk at least 200 meters in the 6-minute walk test (6MWT).
- Cohort 2: this cohort was planned to enroll 4 to 6 ERT-experienced non-ambulatory subjects defined as adults with Pompe disease who are wheelchair-bound and unable to walk unassisted and have been on ERT for \geq 2 years prior to enrollment.
- Cohort 3: this cohort was planned to enroll 5 ERT-naïve ambulatory subjects defined as adults with Pompe disease who have never received treatment with ERT and who are able to walk at least 200 meters in the 6MWT.
- Cohort 4: this cohort was planned to enroll 6 to 8 ERT-experienced ambulatory subjects defined as adults with Pompe disease who have been on ERT for at least 7 years prior to enrollment and are able to walk at least 75 meters in the 6MWT. This cohort was added after Amendment 5 to Protocol ATB200-02.

The 4 study stages are as follows:

- Stage 1 is a 3-period, fixed-sequence, single-ascending dose PK study of ATB200 alone. Safety, tolerability, and PK were evaluated following sequential single-ascending doses of 5 mg/kg, 10 mg/kg, and 20 mg/kg of IV infused ATB200 administered 2 weeks apart. Only subjects in Cohort 1 participated in Stage 1.
- Stage 2 is a 2-period, fixed-sequence, single- and multiple-dose PK study of 20 mg/kg ATB200 co-administered with multiple-ascending doses of AT2221. In Stage 2, safety, tolerability, and PK were evaluated following single- and multiple-ascending dose combinations: 20 mg/kg of IV infused ATB200 co-administered with 130 mg of AT2221 administered orally every 14 days (\pm 3 days) for 3 doses, followed by 20 mg/kg of IV infused ATB200 co-administered with 260 mg of AT2221 administered orally for 3 doses. Only subjects in Cohort 1 participated in Stage 2.

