- Stage 3: Cohort 1 subjects who completed Stages 1 and 2 entered into an extension stage of the study, during which they continued on extended treatment with 20 mg/kg of IV infused ATB200 co-administered with 260 mg of AT2221 administered orally. Additionally, during Stage 3, three new cohorts – Cohorts 2, 3, and 4, were enrolled. Subjects from Cohorts 2, 3, and 4 were treated with 20 mg/kg of IV infused ATB200 co-administered with 260 mg of AT2221 administered orally every 2 weeks. The

duration of Stage 3 was 2 years, and all subjects were evaluated for safety, tolerability, PD, and efficacy. In addition, disease-relevant functional assessments were performed at regular intervals. Key messages from Stage 3 will help support the proof-of-concept based on the efficacy endpoints.

- The Stage 4 treatment period began at the end of Stage 3 and will continue as a long-term extension to provide additional safety and efficacy data until subject withdrawal, regulatory approval, or marketing authorization and/or commercialization in the participating subject's country, or study termination by the sponsor, Amicus Therapeutics (Amicus).

Table 2: Treatment Assignment by Cohort and Stage

Cohorts	Stage 1 (6 weeks)			Stage 2 (12 weeks)		Stage 3 (2 years)	Stage 4 (Until Approval)
	Period 1 Single-dose	Period 2 Single-dose	Period 3 Single-dose	Period 4 3 Multiple Doses Co-administration	Period 5 3 Multiple Doses Co-administration	Multiple Dose, 24 months, Extension Co-administration	Multiple Dose, Long-term, Extension Co-administration
Cohort 1 (n = 11)	5 mg/kg ATB200	10 mg/kg ATB200	20 mg/kg ATB200	20 mg/kg ATB200 + 130 mg AT2221	20 mg/kg ATB200 + 260 mg AT2221	20 mg/kg ATB200 + 260 mg AT2221	20 mg/kg ATB200 + 260 mg AT2221
Cohort 2 (n = 4-6)	NA			20 mg/kg ATB200 + 260 mg AT2221		20 mg/kg ATB200 + 260 mg AT2221	
Cohort 3 (n = 5)	NA			20 mg/kg ATB200 + 260 mg AT2221		20 mg/kg ATB200 + 260 mg AT2221	
Cohort 4 (n = 6-8)	NA			20 mg/kg ATB200 + 260 mg AT2221		20 mg/kg ATB200 + 260 mg AT2221	

Abbreviations: ATB200 = cipaglucosidase alfa; AT2221 = miglustat; NA = not applicable

Note: At least 1 of the 2 sentinel subjects will complete Stage 2, Period 5 and the safety data will be reviewed by the Safety Steering Committee (SSC) before dosing any newly enrolled subjects from Cohorts 2 and 3. The first 2 subjects from Cohorts 2 and 3 will also serve as sentinel subjects for their respective cohorts.

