6.2. General Methodology and Presentation

6.2.1. General Methodology

There will be no inferential statistics as no hypothesis tests were planned for this study. In general, continuous variables will be summarized using descriptive statistics including the number of subjects (n), mean, standard deviation (SD), median, the first quartile (Q1), third quartile (Q3), minimum, and maximum. Unless otherwise stated, these summaries will be provided for the raw values, absolute change from baseline, and the percent change from baseline values. Where appropriate, a 95% confidence interval (CI) for the mean change from baseline will be provided for summary purposes. Categorical variables will be summarized using frequencies (counts) and percentages.

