9.7. Handling of Dropouts or Missing Data

The efficacy and safety analysis will be based on observed values. However, summary at the LAV will be provided for the efficacy analyses (see Section [6.5](#)).

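### The SAP's mean time to first IAR covers only subjects who had an IAR, so it describes onset timing in those subjects rather than time to first IAR in everyone treated

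*SAP*

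**What the plan says.** SAP Section 10.3.3.2 defines the time, in weeks, from the first 20 mg/kg ATB200 + 260 mg AT2221 dose to the first treatment-emergent IAR. It states that "This analysis does not include subjects who have no IARs" and that the times are summarised "to obtain the mean time to the first IAR-TEAE". The summary set in SAP Section 6.2.1 also supplies n and "mean, standard deviation (SD), median, the first quartile (Q1), third quartile (Q3), minimum, and maximum", computed on the same affected subjects. No censoring rule is given; SAP Section 9.7 says only that "The efficacy and safety analysis will be based on observed values". SAP Section 10.3.2 lists time to first IAR among the outputs by treatment group, and SAP Section 6.2.2.3 displays Stage 3 and 4 safety results by cohort.

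Follow-up is not uniform. On Stage 3 the SAP says "duration of Stage 3 was 2 years, and all subjects were evaluated", but Stage 4 is open-ended. On Cohort 4 it says "This cohort was added after Amendment 5 to Protocol ATB200-02". On the end of data collection it says "The expected database lock (DBL) date for the final CSR is 24 July 2024".

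**The concern.** Subjects who never react still contribute information: each was at risk, without an IAR, for a known length of time. Dropping them turns a time-to-event question into a mean among those whose event fell inside their own follow-up. That mean cannot exceed the follow-up available, and with a low, steady hazard it lies close to half of it. Two cohorts with the same IAR hazard but different enrolment dates would show different means, side by side in one table. The title of the section invites the reader to take the figure as the usual time to a first reaction in treated subjects, when many of them may have none.

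**Working it through.** The SAP states no numerical time-to-IAR figure, so there is nothing to reproduce. The check is how the planned mean behaves under stated assumptions.

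**Formula.** For a constant hazard h per week and common follow-up F weeks, the mean time among subjects with an event by F is

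E[T | T ≤ F] = 1/h − F·exp(−hF) / (1 − exp(−hF)).

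It tends to F/2 when hF is small and to 1/h when hF is large. A simulation at h = 0.0025, F = 286 gave 126.0 against 126.1 from the formula.

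**Inputs.** Protocol Section 6.4.2.6 (data cut August 2017) describes two subjects with IARs in just over 400 infusions. At one infusion every 2 weeks that is about 400 × 2 = 800 subject-weeks, so h ≈ 2/800 = 0.0025 per week. This is very imprecise, and the infusions include Stages 1 and 2. Of the follow-up lengths, 104 weeks is the Stage 3 duration and 72 weeks the longest treatment at that cut; 208, 286 and 390 weeks are assumed, because the documents give no follow-up per cohort.

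**Low hazard (h = 0.0025; unconditional mean 1/h = 400 weeks).**

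| F (weeks) | F/2 | Subjects with an IAR | SAP mean (weeks) |
|---|---|---|---|
| 72 | 36 | 16.5% | 34.9 |
| 104 | 52 | 22.9% | 49.7 |
| 208 | 104 | 40.5% | 95.0 |
| 286 | 143 | 51.1% | 126.1 |
| 390 | 195 | 62.3% | 163.8 |

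Doubling F from 104 to 208 multiplies the mean by 95.0/49.7 = 1.91. Raising the hazard four-fold, to 0.01, lowers it only from 49.7 to 43.1 at F = 104 and from 126.1 to 82.6 at F = 286, although the share of subjects reacting rises from 23% to 65% and from 51% to 94%. With the event-free subjects kept and censored, cumulative incidence at 104 weeks estimates 23% whether follow-up is 104 or 286 weeks.

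**Same model, indexed by incidence p (h = −ln(1 − p)/F).** With 5 years of follow-up the mean is 128, 123 and 111 weeks for p = 10%, 30% and 60%. With 2 years it is 51, 49 and 44 weeks.

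**High hazard (h = 0.05).** The mean is 19.4, 20.0 and 20.0 weeks at F = 104, 208 and 286, against 1/h = 20. Follow-up hardly matters.

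**Susceptible fraction.** If 10%, 40% or 80% of subjects are susceptible, with h = 0.05 in those subjects and F = 286, the mean is about 20 weeks each time. It then describes onset timing in affected subjects and says nothing about how many are affected.

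**Enrolment date alone.** A subject with 72 weeks of treatment on 1 August 2017 (day assumed) had about 72 − 12 = 60 weeks since Visit 9 (Day 85). Adding 364 weeks to 24 July 2024 gives 424. From Amendment 5 (16 February 2018) to 24 July 2024 is 336 weeks, the most that Cohort 4 could have. At h = 0.0025 the formula gives 175 and 145 weeks. These are maximum possible follow-ups, not actual ones.

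**The case against.** The SAP states the conditioning openly, plans no hypothesis test and never offers this mean as its measure of IAR risk. Risk is covered elsewhere: SAP Section 10.3.2 gives the number and percentage of subjects with IARs, counts of IARs per subject, and IAR-associated infusions as a share of all infusions in all subjects; SAP Section 10.3 adds adverse event incidence per patient-year. SAP Section 10.3.3.1 plans event rates by onset interval, expressly to see whether IARs fade or appear late. The median, quartiles and range accompany the mean. Cohorts are small (planned at 11, 4–6, 5 and 6–8), so a by-cohort curve will be imprecise.

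All of that stands, and it rules out three stronger readings that a reader might infer:

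- That the mean reflects follow-up rather than risk. It depends on both, and the h = 0.05 case shows it almost free of follow-up.
- That the output cannot show whether IARs are early or late. It describes timing among affected subjects, and Section 10.3.3.1 addresses the wider question.
- That the mean will rest on two people. That count comes from a 2017 cut, before Cohort 4 existed, and not from the planned lock.

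What the objection does not supply is a summary of time to first IAR with IAR-free subjects at risk. None of the other planned outputs gives one, and Section 10.3.3.1 does not define the denominator for its interval rates.

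**Conclusion.** The point holds for this one descriptive summary. The mean in SAP Section 10.3.3.2 is conditional on having an IAR, does not estimate time to first IAR in treated subjects, and should not be compared across cohorts with different follow-up. At a hazard near the interim rate, follow-up is the main driver: 49.7 weeks against 126.1 for 104 and 286 weeks. These figures assume a constant hazard and a common follow-up, rest on a rate from two affected subjects, and are not trial results; if IARs are early and frequent, the dependence on follow-up is slight. It would be wrong to conclude that the SAP leaves IAR risk unmeasured, since frequency and interval rates are planned separately. This is a cheap improvement to the plan and does not undermine the safety evaluation.

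**What to change.** Add to SAP Section 10.3.3.2 a Kaplan-Meier (cumulative incidence) summary of time to first IAR-TEAE in the Safety population, for the total and descriptively by cohort:

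- Start at the first 20 mg/kg ATB200 + 260 mg AT2221 dose.
- Censor IAR-free subjects at the earlier of (a) last dose + 30 days, matching the treatment-emergence rule in SAP Section 10.3, and (b) end of study participation or data cutoff.
- Report cumulative incidence at 6, 12 and 24 months with 95% confidence intervals.

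Keep the event-only times, labelled *onset timing among subjects with an IAR*, with n/N shown for each column.

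The cost is one extra table or figure from data already held, and SAP Section 2 allows changes before database lock. Intervals will be wide, especially by cohort: with no IAR among 5 fully followed subjects, the exact two-sided 95% upper limit is 1 − 0.025^(1/5) = 52%. The total column will be the more useful one.

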10.3.3.3. Analysis by Time After Infusion

IARs and anaphylactic reactions will be analyzed by the time after infusion. Based on the protocol descriptions of immediate-type IARs and late-type infusion reactions, the following time after infusion will be used:

- 0 to < 2 hours, 2 to < 6 hours, 6 to < 12 hours, 12 to < 24 hours (1 day), 1 to < 4 days (96 hours), or the time just before the next dose of study drug.

The event rates and changes in intensity over time (over these intervals) will be summarized as described in Section 6.2.1. This analysis will help to describe the clinical characteristics of IARs and anaphylactic reactions.

10.3.4. Describing Relationship to Study Drug

For each AE entered on the AE eCRF, the reporting investigator was asked to assess the relationship to both infusion drug (ATB200) and capsule (AT2221). The relationship to each study drug will be presented by 2 categories:

- “related,” which includes possibly related, probably related, and definitely related, as reported by the investigator
- “not-related,” which includes unrelated and unlikely related, as reported by the investigator

To describe the overall relationship to study drug, 2 approaches will be presented:

1. Based on the pooling into one designation of the 2 individual relationships to ATB200 and AT2221:
 - a. If the 2 categories of the individual relationships are discordant (ie, “related” to one and “not related” to the other), the pooled designation will be considered “related.”
 - b. If the 2 categories of the individual relationships are concordant (ie, “related” to both, or “not related” to both), the pooled designation will be concordant with the individual categories.
2. Based on the assessment of causality to the individual component, yielding these possible combinations:
 - a. “related” to ATB200 – “related” to AT2221
 - b. “related” to ATB200 – “not related” to AT2221
 - c. “not related” to ATB200 – “related” to AT2221
 - d. “not related” to ATB200 – “not related” to AT2221

10.4. Clinical Laboratory Evaluation

Laboratory data will be collected and processed via a central laboratory, QLab, and presented in standard international (SI) units. Lab data will be summarized using the descriptive statistics described in Section 6.2.1 and presented based on the descriptions in Section 6.2.2.3. Clinical laboratory results collected during Stages 1 and 2 have been reported in iCSR-1 and will not be repeated here unless the underlying data have changed. These results will be referenced in the final CSR.

The rest of this section describes the analysis of laboratory data collected during Stage 2 Period 5 through Stages 3 and 4. The clinical lab parameters are presented in [Table 7](#).

Table 7: Clinical Laboratory Parameters

Serum Chemistry	
ALT	Creatinine
Alkaline phosphatase	GGT
AST	Glucose
Albumin	LDH
Bilirubin, total	Magnesium
BUN	Phosphorous
Calcium, total	Potassium
Carbon dioxide, total (bicarbonate)	Protein, total
Chloride	Sodium
CK	Uric acid
Hematology	
Platelet count	Automated WBC differential
Red blood cell count	Neutrophils
WBC count (absolute)	Lymphocytes
Hematocrit	Monocytes
Hemoglobin	Eosinophils
	Basophils
Urinalysis	
Color	Ketones
Appearance	Blood
Specific gravity	WBC
pH	Nitrite
Protein	Bilirubin
Glucose	Microscopy of sediment
Urine hexose tetrasaccharide (Hex4)	

Abbreviations: ALT = alanine aminotransferase; AST = aspartate aminotransferase; BUN = blood urea nitrogen; CK = creatine kinase; GGT = gamma-glutamyltransferase; LDH = lactate dehydrogenase; WBC = white blood cells

Quantitative laboratory results will be summarized for hematology, serum chemistry, and selected urinalysis parameters. The actual values, absolute change from baseline, and percent change from baseline will be summarized. Figures of mean (\pm SE) absolute change from baseline will be plotted for ALT and AST, and the mean \pm SD values at baseline will be indicated in a legend for the plots.

Laboratory results will be presented in an appendix data listing for each lab panel (chemistry, hematology, and urinalysis). The listing will include the stage, cohort, treatment dose, subject, visit, and parameter. Laboratory values outside of the normal range will be flagged. Categorical urinalysis findings and urine pregnancy results will be presented in appendix data listings only.

The percentage of subjects with specific treatment-emergent laboratory values (ie, lab values collected after the first dose in Stage 2 Period 5) that meet the PDLC criteria shown in [Table 8](#) by parameter will be summarized altogether (over the duration from first dose in Stage 2 Period 5 through Stages 3 and 4 to the DBL date), not by visit. The incidence rates of PDLCs will be presented. Unscheduled visits will be included in evaluating the PDLC summary.

A listing will be provided of subjects meeting the PDLC criteria. If a subject has at least 1 post-baseline value that meets the PDLC criteria for any lab parameter, then all values of that parameter for that subject will be listed. For the PDLCs, it is possible for subjects to appear in both categories for any parameter.

Table 8: Pre-defined Limits of Change Criteria for Clinical Safety Laboratory Data

Laboratory Test	Parameter for ANY Value and LAST Value
Chemistry	
Albumin	Composite: < LLN and > 25% decrease from BL
Bilirubin	Composite: > ULN and > 25% increase from BL
	Absolute Value: > 2X ULN
Bicarbonate	Absolute Value: < 16 mEq/L
Calcium	Composite: > ULN and > 10 % increase from BL
Phosphorus	Composite: < LLN and > 25% decrease from BL
	Composite: > ULN and > 25% increase from BL
Potassium	Composite: < LLN and > 15% decrease from BL
	Composite: > ULN and > 15% increase from BL
Sodium	Composite: < LLN and decrease > 5 mEq/L or more from BL
	Composite: > ULN and increase > 5 mEq/L or more from BL
Uric Acid	Male: absolute value \geq 624.6 mM
	Female: absolute value \geq 505.6 mM
	Composite: < LLN and > 25% decrease from BL
	Composite: > ULN and > 25% increase from BL
ALT	Absolute Value: > 3X ULN
	Absolute Value: > 5X ULN
	Absolute Value: > 8X ULN
AST	Absolute Value: > 3X ULN
	Absolute Value: > 5X ULN
	Absolute Value: > 8X ULN

Table 8: Pre-defined Limits of Change Criteria for Clinical Safety Laboratory Data (Continued)

Laboratory Test	Parameter for ANY Value and LAST Value
Chemistry (Continued)	
ALT > 3X ULN and Tbili > 2X ULN	Composite: ALT > 3X ULN and Tbili > 2X ULN (with the Tbili elevation > 2 X ULN within 30 days of the ALT elevation > 3X ULN)
AST > 3X ULN and Tbili > 2X ULN	Composite: AST > 3X ULN and Tbili > 2X ULN (with the Tbili elevation > 2X ULN within 30 days of the AST elevation > 3X ULN)
CK	Absolute CK \geq 2X ULN or 2X baseline value
Hematology	
Hemoglobin	Male: absolute value \leq 11.5 g/dL
	Female: absolute value \leq 9.5 g/dL
	Change: \geq 2 g/dL decrease from BL
	Change: \geq 2 g/dL increase from BL
Platelets	Absolute value: \leq 75 \times 10 ⁹ /L
	Absolute value: \geq 700 \times 10 ⁹ /L
	Composite: > ULN and increase > 25% from BL
	Composite: < LLN and > 25% decrease from BL
Eosinophils	Absolute value: > 10%

Abbreviations: ALT = alanine aminotransferase; AST = aspartate aminotransferase; BL = baseline; CK = creatine kinase; LLN = lower limit of normal; Tbili = total bilirubin; ULN = upper limit of normal

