APPENDIX 2. POTENTIALLY CLINICALLY SIGNIFICANT GUIDELINES

Criteria for identifying abnormalities as potentially CS are based on the Guidelines for the Division of Neuropharmacological Drug Products, US Food and Drug Administration (revised on April 2, 1987). The laboratory values identified below are not inclusive of all the safety laboratory analytes that will be assessed during this clinical trial. Safety laboratory analytes which are known to be elevated in some adults with Pompe disease (eg, AST, ALT, LDH) and safety laboratory analytes which are not listed below will be reviewed to determine if they are to be noted as potentially CS based on the magnitude of the out of range value as compared to the normal range and the subject's baseline value, and whether the out of range value is coded as CS by the principal investigator.

Laboratory Values		
Variable	Criterion Values	
	Standard Units	SI Units
Chemistry		
SGOT (AST)	$\geq 3 \times$ Upper Limit Normal	
SGPT (ALT)	$\geq 3 \times$ Upper Limit Normal	
Alkaline Phosphatase	$\geq 3 \times$ Upper Limit Normal	
LDH	$\geq 3 \times$ Upper Limit Normal	
BUN	≥ 30 mg/dL	≥ 10.7 μ M
Creatinine	≥ 2.0 mg/dL	≥ 176.8 μ M
Uric Acid	Male ≥ 10.5 mg/dL	≥ 624.6 μ M
	Female ≥ 8.5 mg/dL	≥ 505.6 μ M
Bilirubin (Total)	≥ 2.0 mg/dL	≥ 34.2 μ M
Hematology		
Hematocrit	Male $\leq 37\%$	
	Female $\leq 32\%$	
Hemoglobin	Male ≤ 11.5 g/dL	
	Female ≤ 9.5 g/dL	
Platelets	$\leq 75,000/\text{mm}^3$ or $\geq 700,000/\text{mm}^3$	$\leq 75 \times 10^9/\text{L}$ or $\geq 700 \times 10^9/\text{L}$
Leukocytes	$\leq 2,800/\text{mm}^3$ or $\geq 16,000/\text{mm}^3$	$\leq 2.8 \times 10^9/\text{L}$ or $\geq 16 \times 10^9/\text{L}$
Eosinophils	$\geq 10\%$	
Neutrophils	$\leq 15\%$	
Urinalysis		
Protein	Increase of ≥ 2 units	
Glucose	Increase of ≥ 2 units	
Casts	Increase of ≥ 2 units	

Abbreviations: BUN = blood urea nitrogen; LDH = Lactate dehydrogenase; SGOT (AST) = serum glutamic oxaloacetic transaminase (aspartate aminotransferase); SGPT (ALT) = serum glutamic pyruvic transaminase (alanine aminotransferase)

Vital Sign Values			
Variable	Criteria		Change Relative to Baseline
Heart Rate	≥ 120 bpm	and an	increase of ≥ 15 bpm
	≤ 50 bpm	and a	decrease of ≥ 15 bpm
Systolic Blood Pressure	≥ 180 mmHg	and an	increase of ≥ 20 mmHg
	≤ 90 mmHg	and a	decrease of ≥ 20 mmHg
Diastolic Blood Pressure	≥ 105 mmHg	and an	increase of ≥ 15 mmHg
	≤ 50 mmHg	and a	decrease of ≥ 15 mmHg
Weight			change of $\geq 7\%$ body weight

ECG Values		
ECG parameter	Low	High

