11. CHANGES TO THE STATISTICAL METHODOLOGY PRESENTED IN THE PROTOCOL

Table 11: Changes from the Statistical Analysis Plan That Was Presented for the Second Interim CSR

Protocol Section/Existing Contents	SAP Section/Revision Text	Reason for Change
7.1; 7.2; 7.3 Objectives and Purpose	3.1; 3.2; 3.3 The bulleted items in the objectives were revised for accuracy and clarity.	For clarification
12.4.1 Intent-to-Treat Population: includes all enrolled subjects. Other populations may be defined in the SAP.	6.1.1; 6.1.3; 6.1.4 The SAP uses 'All Enrolled Subjects' population, but no ITT population. The SAP also includes Efficacy and PK populations.	(1) For clarity (2) There may be improper usage of the term ITT analyses, as the study was not randomized.
12.4.4.2; 12.4.4.5 Analyses are organized for: (1) Individual Cohorts, and overall; (2) Combined Cohorts 1, 3, and 4 (for ambulatory subjects); and (3) Combined Cohorts 1 and 4 (for ERT-experienced subjects)	General The SAP is organized as one document with three sub-studies based on the different stages in the study design (Stage 1, Stage 2, and Stages 3 and 4). However, the presentation of results for Stages 3 and 4 is consistent with the way analyses are organized in the protocol.	Organization of SAP is designed to meet the needs of the interim CSR.
12.4.4.2; 12.4.4.3 Summary statistics specified are: n, mean, SD, median, minimum, and maximum.	6.2 The first quartile (Q1) and third quartile (Q3) have been added to the summary statistics.	Q1 and Q3 can help in understanding the data distribution.
12.4.4.3 Safety Analyses	10.1; 10.3 Additional details have been provided for the safety analyses so as to align them to the ongoing pivotal Study ATB200-03.	For clarification and consistency
12.4.4.3 – Safety Analyses Shift changes and shift tables are described for vital signs, clinical labs, ECG based on PCS values in Protocol Appendix 2.	10.4; 10.5; 10.6 No more shift tables. Shift changes are now based on the use of PDLC. Although the PDLC criteria are similar to the PCS, they are not exactly the same.	To keep some level of consistency with Study ATB200-03.

Abbreviations: CSR = clinical study report; ECG = electrocardiogram; ERT = enzyme replacement therapy; ITT = intent-to-treat; PCS = potentially clinically significant; PDLC = pre-defined limits of change; PK = pharmacokinetic; SAP = statistical analysis plan; SD = standard deviation

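### SAP Table 8 prints the absolute uric acid limits in mM where protocol Appendix 2 has the same digits in micromolar, so the two limits as written are 1000 times too high

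*SAP*

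**What the plan says.** SAP Table 8 gives the uric acid limits as "Male: absolute value \geq 624.6 mM" and "Female: absolute value \geq 505.6 mM". The same uric acid block has composite rows, including "Composite: > ULN and > 25% increase from BL" (wording also used for other analytes). Section 10.4 states that laboratory data are "presented in standard international (SI) units". The PDLC criteria feed a by-parameter incidence summary running from the first Stage 2 Period 5 dose to database lock. They also feed a listing: "A listing will be provided of subjects meeting the PDLC criteria".

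Protocol Appendix 2 gives the uric acid limit in standard units as "Male ≥ 10.5 mg/dL", with 624.6 micromolar in the SI column. For women it gives 8.5 mg/dL, with 505.6 micromolar.

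SAP Section 11 replaces the Appendix 2 shift tables with the PDLC approach and comments: "Although the PDLC criteria are similar to the PCS, they are not exactly the same". It describes no change to the uric acid limit. The SAP Introduction says that the SAP's analyses take precedence over the protocol's.

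**The concern.** The two documents use identical four-digit limits with units that differ by a factor of 1000. Because the SAP takes precedence, the micromolar unit in Appendix 2 does not automatically correct Table 8. A limit beyond any possible serum value would give a row of zeros, and in a safety table that looks like a valid finding rather than a broken criterion. What is at stake is whether the two absolute uric acid rows can report anything, and whether subjects who qualify only through those rows appear in the PDLC listing.

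**Working it through.** **Inputs.** From Appendix 2: uric acid 10.5 mg/dL paired with 624.6 micromolar (male) and 8.5 mg/dL paired with 505.6 micromolar (female). From SAP Table 8: 624.6 mM and 505.6 mM. Molar masses are physical constants that the documents do not give: uric acid 168.11 g/mol, creatinine 113.12, bilirubin 584.66, urea nitrogen 28.014 (two nitrogen atoms).

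**Formula.** micromol/L = (mg/dL × 10 / molar mass) × 1000.

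**Step 1: reproduce the protocol's figures.**
- Male: 105 mg/L / 168.11 = 0.6246 mmol/L = 624.6 micromol/L. Agrees.
- Female: 85 mg/L / 168.11 = 0.5056 mmol/L = 505.6 micromol/L. Agrees.
- Creatinine, 2.0 mg/dL: 20 / 113.12 × 1000 = 176.8 micromol/L. Agrees.
- Bilirubin, 2.0 mg/dL: 20 / 584.66 × 1000 = 34.2 micromol/L. Agrees.

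The uric acid result does not depend on the assumed constant. The protocol's own pairs imply 105,000 / 624.6 = 168.1 and 85,000 / 505.6 = 168.1 g/mol.

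**Step 2: read the SAP limits as printed.**
- 624.6 mmol/L × 168.11 g/mol = 105.0 g/L = 10,500 mg/dL, against 10.5.
- 505.6 mmol/L × 168.11 g/mol = 85.0 g/L = 8,500 mg/dL, against 8.5.

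Both ratios are 1000.

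**Step 3: what a program would do.** The SAP does not say whether uric acid is held in micromol/L or mmol/L.
- Data in micromol/L, digits coded without regard to the unit: the limit is 624.6 micromol/L, the protocol's value.
- Data in micromol/L, limit converted as printed: 624,600 micromol/L, so no subject qualifies.
- Data in mmol/L, digits coded: a sample exactly at the protocol limit reads 0.6246 against 624.6, so no subject qualifies.

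**Step 4: does the composite row cover the gap?** Not fully. Take a man who goes from 520 to 630 micromol/L (invented values). He passes 624.6, but his rise is (630 − 520) / 520 = 21%, short of the 25% that the composite row requires.

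**Side check: blood urea nitrogen in Appendix 2.** 30 mg/dL = 300 mg/L; 300 / 28.014 = 10.71 mmol/L = 10,709 micromol/L. The SI column prints 10.7 micromolar, which is 0.0107 mmol/L × 28.014 / 10 = 0.03 mg/dL. The row disagrees with itself by a factor of 1000, in the low direction.

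**The case against.** The strongest reply is that the point turns on one character. A micro sign can become an m when a PDF is read by a program, and the matching digits fit that explanation as well as an author's slip. No correctly rendered micro sign elsewhere in the SAP text settles the matter, although other special characters, such as the Greek alpha, survive. This stands as a reason to check the source page first; the text as supplied reads mM.

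The second reply is that a sensible programmer would not apply an impossible limit. Table 8 mixes units (hemoglobin in g/dL, sodium in mEq/L), so limits have to be matched to data in any case, and the printed digits used on micromolar data give the protocol's limit. That is fair, and it makes an empty row a conditional outcome, not a certain one. It does not make the printed criterion correct.

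A reader might also infer that high uric acid would go unseen in the report. The documents do not support that. The composite row is unaffected by the unit, values outside the normal range are flagged in the listings, and actual values and changes from baseline are summarised. Nor are the PDLC limits real-time alerts; they are criteria for a summary and a listing.

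A sponsor might cite the remark in SAP Section 11 that the two sets of criteria differ. That remark does not mention uric acid, and a deliberate 1000-fold change that keeps every digit is not credible.

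**Conclusion.** The point holds as a unit error in two SAP Table 8 rows. As printed, both absolute uric acid limits are 1000 times those in Appendix 2 and, applied literally, can flag nobody. This assumes that the source page reads as supplied and that the SAP meant to carry over the protocol's limits, which the identical digits indicate. The practical loss is bounded: it reaches subjects who cross the absolute limit without meeting a composite criterion, chiefly those with a high baseline. The study tests no hypotheses and uric acid is not a stopping criterion, so no efficacy result or stopping rule depends on these rows. It is still a wrong reporting threshold in a safety table and should be corrected.

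The blood urea nitrogen slip should not be given equal weight. One might infer that it distorts the safety outputs, or that nearly every sample would be marked. But Table 8 has no urea nitrogen row, the shift tables based on Appendix 2 were dropped, the mg/dL limit stands in the same row, and protocol Section 10.2.11 leaves clinical significance to the investigator. No SAP output is affected.

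**What to change.** - Check the source page of SAP Table 8. If it reads mM, change the unit to micromol/L in the male and female uric acid rows, so that they match Appendix 2.
- Confirm that the PDLC program compares values and limits in the same unit, and record that unit in the analysis dataset specification.
- In Appendix 2, reconcile the SI unit in the blood urea nitrogen row with the mg/dL value beside it, by amendment or by a note to file.

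The cost is two unit corrections in the SAP, one program check and one protocol note. No new threshold is introduced and no data need to be collected.
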